At the end of V2, participants will receive the first set of assigned research cigarettes and will be asked to smoke those cigarettes in their home environment for 7 days; starting on the day after V2. The ordering of flavor of the research VLNCs to be smoked (menthol and non-menthol) will be counterbalanced and assigned prior to Visit 2 (Individuals who complete the session remotely will be scheduled for a pick-up date to get the VLNCs1). During each 7-day period of exposure, participants will be instructed to switch their usual brand cigarette for the assigned research cigarette and will provide daily data on smoking quantity, craving, withdrawal, subjective response, and alternative tobacco product use via twice daily EMA surveys. We will allow for other tobacco product use without specific instruction to align with the real-world scenario, as these products will exist on the market even if a menthol ban and/or a reduced nicotine standard are enacted. Given the high prevalence of dual and poly-tobacco use in this age group, we will examine change in alternative tobacco product use between conditions as a secondary outcome in exploratory analyses, per Co-I [name]'s and [name]'s previous work. Participants will have a 7-day period wash-out period of return to smoking as usual (own brand of cigarette) between the experimental conditions.

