Smoking Sessions 2 and 3 (Visits 3 and 4): Research Cigarettes. Study Visits 3 and 4 (V3-V4) will be identical to each other. Participants will return to the laboratory for V3 and V4 at the end of each 7-day period of using the assigned research cigarette in their home environment, and smoke that assigned research cigarette in the laboratory. At each visit, participants will be asked to abstain from cigarette smoking or other nicotine for > 12 hours (verified by expired CO \leq 6ppm or >50% reduction in CO from baseline, per [name] research. Additionally, prior to smoking participants will be asked when they smoked their last cigarette).²⁴ Before smoking the assigned research cigarette, participants will complete a **cigarette purchase task (CPT)**, a behavioral economics-based measure of cigarette reinforcement, which assesses hypothetical demand for cigarettes across a range of prices, and a **cross-price elasticity purchase task**, which assesses hypothetical demand for experimental cigarettes at increasing prices of an individual's preferred brand of cigarettes. Participants will also complete a **perceived health risk survey** for the study cigarettes, a **predicted behavior questionnaire**, an **expected utility questionnaire**, the **American**

Thoracic Society Questionnaire, and heart rate and blood pressure will be taken before smoking. They will smoke one assigned research cigarette ad libitum at each visit. Puff topography, subjective response, heart rate and blood pressure, and CO boost will be collected. After smoking, participants will complete the **Modified Cigarette Evaluation Questionnaire (mCEQ¹³⁸⁻¹⁴⁰)**, the **Nicotine Drug Effects Questionnaire (N-DEQ)**, the **Duke Sensory Questionnaire (DSQ)**, and the **Minnesota Nicotine Withdrawal Scale (MNWS)**. At the conclusion of visit 4, participants will be asked to participate in a brief assessment to query about satisfaction with and reactivity to the daily EMA survey (**post-lab and post-EMA reactivity questionnaire**).

EXPERIMENTAL TOBACCO MARKETPLACE (ETM)

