Safety: Pregnancy tests will be performed for all female participants prior to engaging in a smoking session. The suicide subscale from the Mini International Neuropsychiatric Interview (MINI)⁹ will be used to evaluate suicide risk. A licensed clinical practitioner will be available to conduct the mental health assessment (see section F). CO level will be obtained at every session to evaluate level of exposure to smoke; a large increase in CO can be a reason for withdrawing a participant from the study. **The Patient Health Questionnaire** 9-item version (PHQ-9)^{10, 11} is a widely used and validated 9-item questionnaire assessing depressive symptoms in the past 2 weeks. This measure will be used for sample description given the high co-occurrence of smoking and depression and will be used to screen out individuals with moderately severe and severe depression. **Brief Medical History** assesses physical and emotional health to establish eligibility for participation. In subsequent sessions, the **Health Changes Questionnaire** asks whether the participant experienced any changes in his/her physical or emotional health since their last visit, including whether they have visited the doctor, the hospital, or whether they have had a change in any of their medications. Any endorsement of a negative health change will be tracked as an adverse event. The **Adverse Events Questionnaire** asks about adverse events experienced since the last visit.

Past 7-day tobacco use will be measured in two different ways. First, at V2 (as part of the cigarette distribution and accountability log) past 7-day tobacco use will be comprehensively assessed using a **Timeline Follow-Back (TLFB)** technique, a reliable calendar-assisted interview validated for estimating daily use

of tobacco and other substances.¹²⁻¹⁴ The TLFB will determine: # cigarettes per day; and frequency and quantity of use of all other tobacco products at baseline to determine the number of cigarettes to be dispensed for the experimental conditions. The **7-day Tobacco Use Questionnaire** will be administered at VLNC2 pick-up (between Visits 3 and 4), where there is a 7-day wash-out period and will ask about past 7-day menthol and non-menthol cigarette smoking, frequency of use of other tobacco products, quit attempts in the past 7-days, and use of other tobacco products to quit.

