Compensatory smoking and/or other tobacco use. The risk of compensatory smoking or increased use of tobacco products will be minimized by tracking daily cigarette and alternative tobacco product consumption assessed via EMA; and evidence of CO increase beyond acceptable levels (assessed at each in-person visit) will result in withdrawal from the study (see DSMP for further details). To minimize the risk of compensatory smoking or increased use of tobacco products, participants' daily smoking will be monitored for any increase as described in detail in the DSMP, and participants will be withdrawn if a marked increase in smoking or other tobacco use is evident. We note that in a recent trial of VLNC cigarettes in which adult smokers were given access to SPECTRUM cigarettes including VLNC doses for 6 weeks and expected to smoke only those cigarettes, there was no evidence of compensatory smoking, neither as measured by cigarettes per day nor by cotinine or toxicant exposure; therefore, we do not expect compensation to occur. Similarly, as noted above, in Co-I [name]'s current field trial of these cigarette doses in adolescents, we have not yet seen significant compensation (N=45 complete as of 2/2018); therefore, this outcome is unlikely. However, we will monitor indicators of increased smoking and alternative tobacco as discussed below and in the DSMP. We will work closely with our consultants to determine decision rules regarding removal from the trial and/or resumption of usual brand cigarettes based on the number of daily reported cigarettes and weekly CO levels to ensure that participants' risk is not increased.

Smoking in the laboratory. Smoking a single cigarette in the lab is used to measure potential compensatory smoking, an important issue under study. Risks related to cigarette puffing will be minimized by limiting this procedure to only one cigarette to and individuals who are smoking "somedays" or "everyday" for > the past 3-months who have no desire to quit. The laboratory where sessions will be completed was constructed with a special ventilation system for quickly removing smoke from the experimental rooms to reduce excess smoke exposure to participants and researchers.

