5. is medically significant, in that it may jeopardize the subject and may require medical or surgical intervention to prevent one of the outcomes listed above.

A hospitalization would not be considered to be a serious adverse event if it was elective, pre-planned, or for a pre-existing condition that did not worsen since starting the study; or for treatment on an outpatient basis for an event not fulfilling any of the definitions of serious given above and not resulting in hospital admission.

Management of AEs/SAEs.

The medical monitor will review all AEs. A study participant may be discontinued from the study if the medical monitor and/or the PI determines it is the best decision in order to protect the safety of a participant. In the event that a participant either withdraws from the study or the investigator decides to discontinue a participant due to an AE/SAE, the participant will have appropriate follow-up medical monitoring. The participant experiencing an AE/SAE will be followed until the problem resolves, stabilizes, or is clearly unrelated to the study cigarettes or procedures. Any AE that remains open will be reviewed and closed during the 30-day follow-up phone call.

For the participant's protection, participants will be withdrawn immediately from the study if any of the following occur:

- 1) Cardiovascular disease (CVD) event: Typically includes MI (heart attack), PTCA (angioplasty/stenting), bypass surgery, stroke, peripheral vascular disease (arterial blockages in arms or legs leading to procedure or surgery). Less common CVD problems would be new cardiac arrhythmias (e.g., new atrial fibrillation) or new valvular disease (e.g., mitral or aortic regurgitation).
- 2) DVT/PE (deep vein thrombosis/pulmonary embolism, i.e., blood clots in the venous system).

- 3) Suicide Attempt: A participant will be withdrawn if he/she attempts suicide at any time during participation in the study.
- 4) Psychiatric Hospitalization: A participant will be withdrawn if he/she is hospitalized for psychiatric reasons at any time during participation in the study.
- 5) Pregnancy: If a participant indicates she is pregnant or has a positive pregnancy test at any session, she will be withdrawn from the study, and this event will remain open until delivery. At that time the medical monitor will contact the participant to ask a few questions about the baby's health and will update the open 'Adverse Event Form'.

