The following will be monitored and can lead to the participant being withdrawn by the PI or Medical Monitor:

- 1) Any hospitalization or debilitation in which participation in the study could be detrimental to the recovery process. This will be self-reported by the participant and will be reviewed by the PI and medical monitor to determine whether continued participation in the study is appropriate.
- 2) If a participant is behaving in an inappropriate or threatening manner, admits to lying about eligibility criteria, including omitting previous medical diagnoses and medications, is participating in other smoking research studies that could affect the primary outcome measures, does not follow study instructions, etc., then the PI can withdraw him/her from the study at her discretion.
- 3) Expired breath carbon monoxide increase: A participant will be withdrawn from the study if the average of two consecutive CO readings during the same visit is 100 ppm or greater.
- 4) Following Co-I [name]'s protocol with adolescents (aged 15-19), we will monitor indicators of increased smoking/tobacco use at each in-person visit, as described above. To minimize the risk of compensatory smoking, participants' daily smoking will be monitored via EMA for any increase as described in detail above, and participants will be withdrawn if a marked increase in smoking is evident. Evidence of marked increase in smoking or tobacco use: A participant will be withdrawn from the study if s/he meets the following criteria for two consecutive study visits.
 - Expired breath carbon monoxide increase: If during a laboratory session his/her CO measurement is as follows (based on CO measurement at baseline):
 - i. CO is greater than 50 ppm if CO at Baseline (Visit 1) is <20 ppm.
 - ii. CO is greater than 60 ppm if CO at Baseline (Visit 1) is 20 – 34 ppm.
 - iii. CO is greater than 70 ppm if CO at Baseline (Visit 1) is 35 – 49 ppm.
 - iv. CO is greater than 80 ppm if CO at Baseline (Visit 1) is 50 – 64 ppm.
 - v. CO is greater than 90 ppm if CO at Baseline (Visit 1) is 65 – 80 ppm

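### The two-visit CO withdrawal rule cannot act on a rise that starts on the study cigarettes until both supplies are used, and then it only removes follow-up data

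*Combined protocol and SAP*

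**What the plan says.** Item 4 of the monitored withdrawal criteria (section K) sets five CO limits according to the Visit 1 reading: above 50 ppm if baseline was under 20, above 60 for 20–34, above 70 for 35–49, above 80 for 50–64 and above 90 for 65–80. The rule is: "A participant will be withdrawn from the study if s/he meets the following criteria for two consecutive study visits".

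The exposure schedule is given elsewhere:
- Smoking Session 1 (V2): "At the end of V2, participants will receive the first set of assigned research cigarettes".
- Smoking Sessions 2 and 3: "Participants will return to the laboratory for V3 and V4 at the end of each 7-day period of using the assigned research cigarette".
- Measures Descriptions places the second supply at "VLNC2 pick-up (between Visits 3 and 4), where there is a 7-day wash-out period".

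Other routes to stopping exist:
- Item 4 also says that "daily smoking will be monitored via EMA for any increase as described in detail above".
- Item 3 acts at one visit, "if the average of two consecutive CO readings during the same visit is 100 ppm or greater".
- Section I.2, on compensatory smoking, says: "We will work closely with our consultants to determine decision rules regarding removal from the trial and/or resumption of usual brand cigarettes".
- Management of AEs/SAEs allows safety discontinuation: "A study participant may be discontinued from the study if the medical monitor and/or the PI determines it is the best decision".

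Under Desire to Quit Smoking, participants who give up the study cigarettes stay in the remaining EMAs, the ETM and the 30-day follow-up. Item 4 has no such provision.

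**The concern.** Item 4 is meant to limit compensatory smoking on VLNCs. Each VLNC has only one visit, at the end of its 7 days, so a rule needing two consecutive visits can be met only after both periods are over. At that point withdrawal protects nobody from study smoking.

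What it does remove is data. V5 supplies ETM 1 and 2, the source of the Aim 3 primary outcome. The 30-day contact supplies ETM 3 and the check that smoking has returned to baseline. The loss would depend on how the participant responded to the study cigarettes, and it would fall on the people for whom that check matters most. The V5 tasks are hypothetical and no cigarette is smoked there, so keeping these participants would add no study smoking.

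**Working it through.** **Calendar.** I rebuilt it from the stated 7-day blocks, with V1 as day 0:
- V2: day 7, after 7 days of usual brand
- V3: day 14, after VLNC period 1
- Second pick-up: day 21, after the wash-out
- V4: day 28, after VLNC period 2
- V5 follows (gap not stated; it does not affect the result), then the contact 30 days later.

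Check against the plan: EMA days = 7 + 7 + 7 = 21, which matches the 21 monitoring days given under Duration and number of study visits.

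**VLNC days left when the rule is met** = 14 − VLNC days used by the second visit of the pair.

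| Pair | VLNC days left | Condition | Assessments lost |
|---|---|---|---|
| V2+V3 | 14 − 7 = 7 | CO already over the limit on usual brand, before any supply | not a VLNC-onset rise |
| V3+V4 | 14 − 14 = 0 | rise starts in period 1 | ETM 1, ETM 2, ETM 3, 30-day survey |
| V4+V5 | 14 − 14 = 0 | rise first seen in period 2 | ETM 3, 30-day survey |

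For comparison, acting on one exceedance at V3 could spare 14 − 7 = 7 of 14 days.

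**How often this could happen.** The plan gives no expected count, so I looked at what a trigger requires. The abstinence check before smoking accepts CO of 6 ppm or less, or a fall of more than 50% from baseline. The highest accepted CO is therefore just under max(6, baseline/2), taken here at the top of each band with whole-number readings. The rise needed from one cigarette must exceed limit − that value.

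| Baseline band (ppm) | Highest abstinent CO | Limit | Rise needed, more than |
|---|---|---|---|
| under 20 | 19/2 = 9.5 | 50 | 40.5 |
| 20–34 | 34/2 = 17 | 60 | 43 |
| 35–49 | 49/2 = 24.5 | 70 | 45.5 |
| 50–64 | 64/2 = 32 | 80 | 48 |
| 65–80 | 80/2 = 40 | 90 | 50 |

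Lower in each band the required rise is larger. A V3+V4 trigger needs such a rise, or failed abstinence, at both visits. V4+V5 is rarer still, because nothing is smoked at V5.

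**Whether another rule fills the gap.** Section I.2 refers to the DSMP for the details of daily-smoking monitoring, and the DSMP refers back to the text above it. Neither gives a threshold, and section I.2 leaves the decision rules on daily cigarettes and weekly CO to be settled. Item 3 is numerical but starts at 100 ppm, above every item 4 limit.

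**The case against.** The strongest reply is that the finding is nearly empty in practice. Two one-cigarette rises of more than 40 to 50 ppm are improbable, and inability to abstain before visits is itself an exclusion criterion. No bias or loss of power has been shown. This stands, and it is why the point is minor.

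The CO rule is also not the only safeguard. EMA runs twice daily in both VLNC weeks, and the text says participants will be withdrawn for an evident marked increase. Supply is capped at 125% of baseline consumption (C.4.f). The team meets weekly, so a meeting would normally fall in the wash-out. Section I.2 already mentions a return to usual brand as an alternative to removal, and the lead-in to the list describes these criteria as ones that can lead to withdrawal. All of this is in the plan, and earlier action is possible. But the EMA route has no threshold and the rest is discretionary. The cap limits the number of study cigarettes but not usual-brand or other tobacco use. The lead-in conflicts with item 4's own mandatory wording.

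Section I.1 speaks of CO at weekly in-person visits. If the second pick-up counted as a visit with a CO reading, V3 plus pick-up could trigger with 7 days left. The plan lists only a questionnaire there, the pick-up may be curbside, and it follows a week of usual brand, so that reading is not supported.

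Finally, requiring two visits guards against acting on one stray reading, and withholding a second supply loses that person's menthol versus non-menthol contrast. Both points are fair, and they favour a review after one exceedance over automatic withdrawal.

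**Conclusion.** The concern holds within its scope: item 4's numerical CO rule, applied to a rise that begins on the research cigarettes. The rule cannot be met before V4, when 0 of 14 VLNC days remain. A V3+V4 trigger costs V5 and the 30-day contact; a V4+V5 trigger costs the 30-day contact only. It does not follow that participants lack any earlier protection, only that such protection below 100 ppm is unquantified or discretionary.

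The timing result rests on the stated visit schedule and on the second pick-up not being a CO visit. The expectation that triggers are rare rests on the abstinence check being applied. Severity is minor: the number affected is probably very small.

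**What to change.** Amend section K in two places.

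1. In item 4, state that meeting the criterion stops the dispensing and smoking of research cigarettes, while the participant stays in V5 and the 30-day follow-up, as already provided for those who choose to stop the cigarettes. Analyse their data under the assigned sequence.
2. Add that a single exceedance of the existing item 4 limits at V3 leads to review by the PI and medical monitor during the wash-out, before the second supply is released. Item 5 already uses this review for out-of-range vital signs.

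Leave the 100 ppm rule and discretionary safety discontinuation unchanged.

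The cost is a minor amendment with no new visit, measure or threshold. There may be a few extra reviews and possibly a few withheld second supplies, and those participants would have no second-period VLNC data.

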Smoking Session 1 (V2): Usual Brand Smoking. At the end of the 7-day baseline period of usual brand smoking, > 12-hour abstinent smokers (expired CO \leq 6ppm) or >50% reduction in CO from baseline, per Co-I [name] research²⁴ will return to the laboratory to assess absolute reinforcing value (ARV) of their usual brand cigarette by having participants smoke one of their usual brand cigarettes (ad libitum) through a transducer-based smoking topography data collection device. The instrument records puff volume, duration and velocity and inter-puff interval for each puff and their aggregate averages. These puff topography measures are useful indices of smoke exposure and are sensitive to differences in smoking behavior that may occur between different cigarette flavoring types.^{59,61,124} Puff topography measures will be used to examine whether increased puff volume, duration, and lower inter-puff interval differ across cigarettes as a measure of compensation. Prior to smoking participants will be asked when they smoked their last cigarette. Immediately before and after smoking the following measurements will be taken: heart rate and blood pressure will be assessed (heart rate, but not blood pressure, will be collected for remote sessions), and exhaled carbon monoxide (CO boost).

Subjective response to smoking (craving reduction, psychological reward, satisfaction, sensory effects) using the **Modified Cigarette Evaluation Questionnaire (mCEQ)**¹³⁸⁻¹⁴⁰ in addition to the **Nicotine Drug Effects Questionnaire (N-DEQ)**, the **Duke Sensory Questionnaire (DSQ)**, and the **Minnesota Nicotine Withdrawal Scale (MNWS)** will be measured immediately after smoking. Exhaled CO will be collected via a Smokerlyzer CO detector (Bedfont Scientific LTD), and measured in ppm immediately before and 10 minutes after smoking. CO boost has been used in previous studies^{141,142,143} to index smoke exposure, and will be calculated as the difference between pre- and post-smoking levels.

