Before smoking the assigned research cigarette, participants will complete a **cigarette purchase task (CPT)**, a behavioral economics-based measure of cigarette reinforcement, which assesses hypothetical demand for cigarettes across a range of prices, and a **cross-price elasticity purchase task**, which assesses hypothetical demand for experimental cigarettes at increasing prices of an individual's preferred brand of cigarettes. Participants will also complete assessment of nicotine withdrawal and craving prior to smoking using the **Minnesota Nicotine Withdrawal Scale (MNWS)**¹⁵ and the **Questionnaire on Smoking Urges**¹⁶. Heart rate and blood pressure will be taken before smoking (some measurements may not be taken if sessions are completed remotely). After smoking, participants will complete assessments of subjective response to smoking with the **modified Cigarette Evaluation Questionnaire (mCEQ)**, the **Duke Sensory Questionnaire (DSQ)**, and the **Nicotine Drug Effects Questionnaire (NDEQ)**. Participants will also complete the MNWS again.

The **Predicted Behavior Questionnaire** will be asked at the beginning of Visits 3 and 4, prior to when the VLNC is smoked. It asks participants to indicate their intentions to use cigarettes and other tobacco products when cigarettes have lower nicotine content and come menthol or non-menthol flavor. The **Expected Utility Questionnaire** will also be administered at Visits 3 and 4, before participants smoke. This questionnaire asks the degree to which participants would use the study cigarettes they just smoked for the past week (menthol or non-menthol) would help them quitting, be less dangerous than smoking, give up tobacco use, smoker fewer cigarettes, etc.

Participants will report their perceptions of the health risks associated with both their usual brand and their study cigarette brand using the **Perceived Health Risks Assessment**.¹⁷

ECOLOGICAL MOMENTARY ASSESSMENT (EMA)

C.5 EMA Procedure. Participants will record cigarette smoking and alternative tobacco use, craving, symptoms of withdrawal, and subjective ratings (e.g., satisfaction, reward, craving reduction, physical sensations like throat hit) associated with smoking the most recent cigarette in response to 2 random prompts to their phone each day. We will use a mobile EMA application, in which participants answer a set of survey questions on their cell phone by selecting

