- 5) At each session, heart rate and blood pressure (or heart rate only if taken remotely) will be taken. Individuals who show heart rate and blood pressure out of range will be rescheduled. A note will be recorded in REDCap if a participant is rescheduled due to out of range score. If a participant shows out of range vitals on two consecutive visits, this will be reviewed by the PI and medical monitor to determine whether continued participation in the study is appropriate. Blood pressure acceptable range: SBP <90

or >140 mmHg; DBP >90 or <50 mmHg. Heart Rate acceptable range: bpm <49- >100 bpm.

Desire to Quit Smoking

We will query about desire to quit smoking at screening, each in-person visit (or virtual session), and at the follow-up. Those who report a desire to quit smoking after study enrollment will be asked if they still want to receive the study cigarettes. This is because use of reduced nicotine cigarettes could help reduce craving and increase the odds of successful smoking cessation among smokers according to findings published by Co-I [name].²⁷ Individuals will also be told at consent and reminded again at each in-person visit that they can decline to continue using the study cigarettes at any time, and still remain enrolled in the study and undergo the study assessments. This will reduce the potential for incentivizing continued smoking. Those who do not want to continue receiving the study cigarettes will no longer be dispensed study cigarettes and will be retained in the study with no penalty and will continue to complete all subsequent EMAs, the ETM, and the 30-day follow-up. Retaining individuals who have stopped using the study cigarettes, or who report a desire to quit smoking and wish to use VLNCs, are vital to informing the outcomes of the study. All participants will be given smoking cessation resources at their request, upon completion of the in-person/virtual study visits (Visit 5), and again at the 30-day follow-up (in-person or on the phone).

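### Section K, item 5 labels as acceptable the blood pressures beyond its printed cut-points, and its heart rate entry, the only vital-sign limit in remote sessions, has no single reading

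*Combined protocol and SAP*

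**What the plan says.** All the numeric vital-sign limits stand in the combined protocol and SAP, Section K, in item 5 of the list of findings that are monitored and can lead to withdrawal.

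- **Measurement:** "At each session, heart rate and blood pressure (or heart rate only if taken remotely) will be taken".
- **First consequence:** "Individuals who show heart rate and blood pressure out of range will be rescheduled".
- **Second consequence:** "If a participant shows out of range vitals on two consecutive visits, this will be reviewed by the PI and medical monitor", to decide whether continued participation is appropriate.
- **Limits:** "Blood pressure acceptable range: SBP <90", continuing over a page break with "or >140 mmHg; DBP >90 or <50 mmHg. Heart Rate acceptable range: bpm <49- >100 bpm".

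Other sections order the measurements but give no numbers. Smoking Session 1 (V2) says "heart rate and blood pressure will be assessed (heart rate, but not blood pressure, will be collected for remote sessions". Smoking Sessions 2 and 3 (Visits 3 and 4) say "heart rate and blood pressure will be taken before smoking". Measures Descriptions says "Heart rate and blood pressure will be taken before smoking (some measurements may not be taken if sessions are completed remotely". Section F, exclusion criterion 2c, covers self-reported, clinically significant hypertension, also without a number.

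**The concern.** Blood pressure and heart rate fail in different ways.

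**Blood pressure.** The figures under the label *acceptable range* are two outer tails: below a lower cut-point or above an upper one. The action rule sends away people who are out of range. Taken together, the two statements pass participants in the tails and reschedule those between the cut-points. They also fit poorly with Section F, which excludes self-reported hypertension.

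**Heart rate.** The entry has the same outward-pointing signs but a dash where blood pressure has *or*. It may be reversed in the same way, or it may be a badly typed interval. The text does not settle which.

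The threshold is applied at each session. It decides whether the session goes ahead and, after two consecutive failures, whether the investigator and medical monitor review continued participation. Staff who follow the text get a result at odds with its evident purpose; staff who correct it mentally depart from a plan that Section K says was approved by NIH/NIDA officials. In remote sessions there is no blood pressure limit to fall back on.

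**Working it through.** No sample-size or error-rate figure is involved. The check applies the printed inequalities as written and compares the result with the same cut-points read as limits for being out of range.

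**Inputs (Section K, item 5).** Acceptable SBP: below 90 or above 140. Acceptable DBP: above 90 or below 50. Heart rate: below 49, a dash, above 100. Action: out of range means reschedule.

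**Step 1: blood pressure.**

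| Reading | SBP in printed acceptable set? | DBP in printed acceptable set? | Action as printed | Action if the figures are out-of-range limits |
|---|---|---|---|---|
| 85/45 | yes | yes | proceed | reschedule |
| 90/50 | no | no | reschedule | proceed |
| 120/80 | no | no | reschedule | proceed |
| 140/90 | no | no | reschedule | proceed |
| 150/95 | yes | yes | proceed | reschedule |
| 180/110 | yes | yes | proceed | reschedule |

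All six classifications reverse with the reading. Item 5 also leaves open whether one abnormal value is enough. The six pairs avoid that question because both components fall on the same side.

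Whole-number values that the printed label puts out of range:

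- SBP 90 to 140: 140 − 90 + 1 = 51.
- DBP 50 to 90: 90 − 50 + 1 = 41.

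**Step 2: heart rate, three readings.**

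- Dash as *or*: 45 and 110 bpm are acceptable and 70 is not. The values out of range are 49 to 100, which is 100 − 49 + 1 = 52 values.
- Both signs together: no number is both below 49 and above 100, so no value is acceptable.
- Interval from 49 to 100: 70 is acceptable, 45 and 110 are not, and label and limits agree.

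**Step 3: could this come from text extraction?** A page break splits the SBP entry. The DBP and heart rate entries each stand on an unbroken line, and DBP shows the same reversal, so the break did not create it.

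**Step 4: remote sessions.** Of the three limits (SBP, DBP, heart rate), only heart rate applies, and it is the entry without a single reading.

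**Side note, not part of the main point.** Item 4 of the same list sets carbon monoxide tiers without saying whether they use the reading before or after smoking; the V2 procedure takes both. A pre-smoking reading that passes the abstinence check is at most 6 ppm or less than half the baseline. For a Visit 1 value up to 80 ppm it is therefore below 80 / 2 = 40 ppm, while the lowest tier is above 50 ppm. Such a reading can never reach a tier. Post-smoking readings, failed abstinence checks and Visit 5 readings still can.

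**The case against.** The strongest reply is that this is a labelling slip whose intent is plain. Anyone applying it literally would reschedule 120/80 at the first visits and notice at once. Nothing suggests that the rule is run in reverse, and no automatic withdrawal depends on it. This stands, and it limits the point to a text correction. It does not remove the need for one, because a safety threshold should not rely on each reader to repair it.

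On heart rate, all three readings share the cut-points 49 and 100, the empty reading is contrived, and one ordinary reading has no conflict. That is fair, and it is why the entry is called unclear and not reversed. Extraction may have altered some comparison signs, so the heart rate string should be checked against the source file. That doubt does not help blood pressure, where the signs and the word *or* are consistent.

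Remote participants also have other safeguards: expired CO with its own withdrawal limits, health-change and adverse-event questionnaires, and immediate withdrawal after a cardiovascular event. These stand, but none of them sets a blood pressure or heart rate limit.

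Finally, the counts of 51 and 41 values describe the printed rule. They are not numbers of participants affected.

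**Conclusion.** The point holds. The blood pressure rule is wrong as written: label, inequality signs and rescheduling sentence cannot be applied together without passing the tails and rescheduling everyone between the cut-points (SBP 90 to 140, DBP 50 to 90). The heart rate entry does not define one rule: 52, 0 or all whole-number values change status against the ordinary interval or cease to qualify, depending on the reading, and it is the only vital-sign limit in remote sessions.

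The conclusion assumes that the comparison signs were read correctly from the source, and that no vital-sign limits stand in material outside the text reviewed. It does not assume that any participant was misclassified, and it takes no view on which limits are clinically right. This is an internal inconsistency in a safety threshold, worth correcting and cheap to correct.

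**What to change.** In Section K, item 5, reconcile the label with the limits for SBP, DBP and heart rate, and print the heart rate entry so that it has one reading, including for remote sessions. State in the same edit whether a single abnormal vital sign triggers rescheduling. The limits are for the sponsor and medical monitor to confirm; none is proposed here.

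Two minor clarifications could go into the same amendment. State which CO reading the tiers in item 4 use. Reconcile the description of EMA monitoring for increased smoking: Section I.2 defers the detail to the monitoring plan, and the monitoring plan points back to earlier text. Neither gives an EMA criterion, although Section I.2 does say that decision rules will be worked out with the consultants.

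The cost is a wording amendment to the IRB, listed among the protocol changes in the annual monitoring report to NIDA. It needs no new procedure or data collection.
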